A comparison of Mepitel Ag vs antibiotic ointment when used with a soft cast technique for the treatment of pediatric hand and foot burns, a prospective study

Protocol #: 15-1828

April 8, 2016

COMIRB Protocol

COLORADO MULTIPLE INSTITUTIONAL REVIEWBOARD
[name] [contact] [contact]

Protocol #: 15-1828

Project Title: A comparison of Mepitel Ag vs antibiotic ointment when used with a soft cast technique for the treatment of pediatric hand and foot burns, a prospective study

Principal Investigator: [name], MD

Version Date: 3/30/16

- I. **Hypotheses:** Mepitel Ag in combination with the soft cast technique improves wound healing in pediatric partial to deep partial thickness hand and foot burns by decreasing the length of healing time, decreasing the risk of yeast infection, and decreasing pain associated with multiple dressing changes.
- II. **Specific Aims:**
 - 1) To examine the efficacy of Mepitel Ag for use in pediatric partial to deep partial thickness hand and foot burns.
 - 2) To evaluate Mepitel Ag to triple antibiotic ointment when used in combination with a soft cast technique comparing healing time, yeast infection rates and pain levels at time of dressing change.

II. Background and Significance:

There is currently no gold standard dressing when it comes to treating hand or foot burns, specifically in the pediatric population. Our institution currently utilizes a soft cast technique (SCT) on all of our hand and foot burns. The SCT provides optimal positioning of the wounded hand or foot, allows for a moist wound environment, and offers protection of the injured extremity as the wound heals. Our current SCT uses triple antibiotic ointment (TAO) impregnated Adaptic gauze, kling or kerlex, cast padding, gypsoma plaster, soft cast material, and coban. This dressing is applied two to three times during the first 2 weeks post injury. To reduce the risk of the development of yeast overgrowth, the underlying dressing is changed to nystatin impregnated Adaptic gauze, kling or kerlex, cast padding, gypsoma plaster, soft cast material, and coban for the remainder of treatment time or until OR is indicated for surgical debridement and grafting of wounds..

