This is due to the fact that “soft silicone dressing have been shown to prevent trauma to the wound bed and periwound skin and have been described as ‘atraumatic’”.¹⁴ Other benefits of soft silicone dressings include the ability to conform to anatomical contours, a reduction in scar development, and reduced overall cost secondary to improved wound healing and need for less frequent dressing changes.¹⁴

Mepitel Ag, a hybrid type soft silicone dressing impregnated with a silver compound was recently approved for use in partial thickness burns and partial and full thickness grafts.¹⁵ This combination of soft silicone and silver provides a relatively pain free dressing with broad spectrum antibiotic coverage. The aim of this study is to demonstrate that Mepitel Ag in combination with a soft cast technique is a superior alternative to antibiotic ointment impregnated gauze and soft cast for the treatment of pediatric hand and foot burns due to decreased healing time, decreased patient pain and lower yeast infection rates.

IV. Research Methods

A. Outcome Measure(s):

Primary outcomes utilized in this study include overall wound outcome, measured in length of days to re-epithelialization or need for surgical intervention, clinical assessment and wound progression photographs. Secondary outcomes include number of patients requiring surgical debridement, presence of infection based on odor, rash, deep red appearance or puritis. These wounds will not be cultured, patient pain level with dressing change based on the FLACC (Face, Legs, Activity, Cry, Consolability) scale, parents perceived level of pain, pain level at home based on family reported pain and pain medication use. We will also assess cost effectiveness of dressings including the number of clinic visits, number of soft casts, and the cost and amount of dressings used over the course of treatment.

B. Description of Population to be Enrolled:

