Patients to be included in this study will be all Children's Hospital Colorado burn patients between the ages of 31 days and 18 years with newly diagnosed partial to deep partial or full thickness hand or foot burns, including bilateral or unilateral injury. Each injured extremity will serve as a separate data point. Exclusions include age > 18 years at start of study, silver allergy, silicone allergy, electrical or chemical burn, past medical history of immunodeficiency disorders such as diabetes mellitus, AIDs, or HIV, pregnant women, prisoners children under the protection of the department of human services, and the decisionally challenged.

C. Study Design and Research Methods

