Analysis Plan: Demographic and clinical characteristics will be summarized and compared between the two treatment groups using chi-squared and two-sample t-tests for categorical and continuous data, respectively. For analysis of the primary outcome, time to wound healing, we will use Kaplan-Meier curves, the log-rank test and a Cox proportional hazards model to determine the difference in days to re-epithelialization between the TAO and Mepitel Ag soft cast methods. Patients that require surgical intervention will be censored at the time of surgery. Logistic regression will be used to analyze the secondary outcomes, need for surgical debridement and occurrence of yeast infection. Pain level outcomes and pain medication use will be compared using two-sample t-tests and chi-squared tests. Cost effectiveness outcomes will also be analyzed.

1. Sample size: A statistical power analysis was performed to estimate power, based on results reported in A Soft casting Technique to Manage Pediatric Hand Burns: Less Pain, Greater Gain.²² Considering the simplest between group comparison and assuming a standard deviation of 0.3, alpha of 0.05 and 50 subjects per group there is over 90% power to detect a difference of 2 days between the treatment groups. Thus, we expect that our proposed sample size of 100 burns will be adequate for the main objective of this study.

G. Summarize Knowledge to be Gained:

To demonstrate that Mepitel Ag in combination with a soft cast technique improves wound healing in pediatric partial to deep partial thickness hand and foot burns by decreasing the length of healing time, decreasing the risk of yeast infection, and decreasing pain associated with dressing changes.

H. References:

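### Censoring burns at surgery makes one minus Kaplan-Meier overstate the proportion healed without surgery; the log-rank and Cox results need a cause-specific reading and stratification by severity

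*Combined protocol and SAP*

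**What the plan says.** Section IV.F makes time to wound healing the primary outcome, to be analysed by "Kaplan-Meier curves, the log-rank test and a Cox proportional hazards model". It then adds: "Patients that require surgical intervention will be censored at the time of surgery". It names no competing-risk method, strata, covariates or sensitivity analysis for surgery. Surgery appears again only as a secondary outcome: "Logistic regression will be used to analyze the secondary outcomes, need for surgical debridement and occurrence of yeast infection".

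Section IV.A differs. There the primary wound outcome is "measured in length of days to re-epithelialization or need for surgical intervention", and surgery is listed a second time: "Secondary outcomes include number of patients requiring surgical debridement".

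Three places link surgery to depth or failure to heal:
- Background and Significance describes dressings continuing "until OR is indicated for surgical debridement and grafting of wounds".
- Section IV.B admits "newly diagnosed partial to deep partial or full thickness hand or foot burns".
- In the severity scale of section IV.C, grade 7 carries a note that a graft may be needed.

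Section IV.C balances randomization on burn severity; one of its sentences adds age.

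**The concern.** Kaplan-Meier treats a censored burn as one that would go on to heal like the burns still under observation. A burn taken to surgery can no longer heal without surgery, so the curve does not estimate the proportion healed without surgery. A reader who takes it that way will see too high a figure in any arm where healings follow a surgery. If surgery comes before the median, the median healing time can also be too early.

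The comparison of arms is a separate matter. If surgery selects slow healers, and its rate, timing or selection differs by arm, the censored comparison can favour one dressing although healing is identical. Section IV.E acknowledges that staff preference for a dressing could cause bias, so such a difference is conceivable. The planned logistic regression compares surgery rates only and cannot show a difference in timing or selection.

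**Working it through.** **The plan's own figure.** The plan gives no surgery rate and no healed proportion. Its only calculation is power: 2 days, SD 0.3, 50 per group. The standard error is 0.3 × √(2/50) = 0.06 and 2/0.06 = 33, so power is effectively 100% and the stated figure of over 90% is met. It does not bear on this point.

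**Curve, no distribution assumed.** Of 50 burns, 10 have early surgery and 40 then heal. Kaplan-Meier ends at 100%; the truth is 40/50 = 80%. Its median is the 20th healing, whereas half of all 50 burns have healed only at the 25th.

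**Curve, closed form (assumed).** Healing time is log-normal, median 14 days, log-SD 0.45, so F(t) = Φ(ln(t/14)/0.45), F(14) = 0.500 and F(21) = 0.816. A share of 0.184 needs more than 21 days.
- *Half of these slow burns have surgery at day 14 (9.2%).* At risk just after: 0.500 − 0.092 = 0.408. Healing from day 14 to 21: 0.816 − 0.500 = 0.316. Kaplan-Meier survival at day 21: 0.500 × (0.408 − 0.316)/0.408 = 0.113. The curve reads 88.7%; 81.6% have healed without surgery.
- *82% of them have surgery at day 14 (15.1%).* 0.500 × (0.349 − 0.316)/0.349 = 0.047. The curve reads 95.3% against 81.6%.
- *Surgery in 9.2%, chosen at random among unhealed burns at day 14.* The curve reads 81.6%; the proportion healed without surgery is 0.500 + 0.408 × (0.316/0.500) = 75.8%.
- *Median.* With 15.1% surgery at day 10 the Kaplan-Meier median is 13.2 days against 14.0. Surgery at day 14 leaves it unchanged.

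**Curve, second model (assumed).** Constant hazards, median healing 12 days, λ = ln 2/12 = 0.0578. One minus Kaplan-Meier at day 21 is 1 − exp(−21λ) = 70.3%. If a share p eventually has surgery, cumulative incidence is (1 − p)[1 − exp(−λt/(1 − p))]. For p = 5, 10, 20 and 30% this gives 68.5, 66.6, 62.4 and 57.6%: overstatement of 1.8 to 12.6 points.

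**Tests, simulated with severity balanced as section IV.C plans (all assumed).** Per arm: 20 partial, 20 deep partial and 10 full thickness burns; medians 11, 16 and 26 days; log-SD 0.30; identical healing in both arms. In the table, follow-up is to day 21. Ranges span separate runs; a single figure is one run. The nominal tail is 2.5%.

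| Surgery in the two arms | False wins, unstratified log-rank, one tail |
|---|---|
| Equal rate (15.1%), day 10 v day 18 | 8.7–9.5% (earlier-surgery arm) |
| Equal rate (15.1%), day 5 v day 20 | 22.4% (earlier-surgery arm) |
| 16.4% v 5.5%, day 14 | 5.0–5.8% (higher-surgery arm) |
| 14.7% v 7.3%, day 14 | 2.5–2.6% |
| 10.9% v 7.3%, day 14 | 0.9% |

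**Stratification, same model, follow-up to day 42.**
- *No surgery:* the unstratified test rejects in 0.2–0.3% per tail, the stratified test in 2.3–3.3%.
- *Surgery depends on category only (25.7% v 7.2%):* Cox hazard ratio 1.16 unstratified, 1.00 stratified; the truth is 1.00.
- *Surgery takes slow healers within category (15.8% v 3.8%):* hazard ratio 1.17 either way. False wins are 3.8–4.2% unstratified and 10.6–11.9% stratified.

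**The case against.** The strongest reply is that the plan asks for a difference in days, not a healed proportion. Log-rank and Cox with censoring at surgery are legitimate cause-specific analyses, surgery is compared separately, and the median need not move. This stands for the tests. It does not rescue the curve: Kaplan-Meier is a planned display, and it will be read as the proportion healed.

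A reader might infer something stronger: that the primary test is seriously inflated, or that it favours a particular dressing. The documents do not support that. They give no surgery rate, no timing and no difference by arm, and the limitation on staff preference does not mention surgery. Unequal surgery that is unrelated to prognosis does not bias the hazard comparison, and neither does an identical surgery rule in both arms. Randomization is balanced on severity, and simulations that ignore this exaggerate the false-win rate. With the balance kept, moderate rate differences largely fail to push the unstratified test above its nominal level, though large timing differences still do.

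Two further objections stand. That the tests are unstratified is inferred from silence; section IV.F does not exclude strata. And stratifying does not cure selection within a severity category.

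**Conclusion.** The curve problem is certain in direction and needs no difference between arms. Its size depends on surgery rates that the documents do not give: about 2 to 14 points at day 21 across the assumed cases with 5 to 30% surgery. Bias in the comparison of arms is possible but unquantified. Under the assumed balanced model, about 9% in one 2.5% tail for surgery at day 10 against day 18 illustrates a large timing difference; it does not predict this trial.

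The case for stratifying rests mainly on efficiency and correct level: after balanced randomization an unstratified test is very conservative (about 0.2% per tail in the assumed model without surgery). It removes only the bias that comes from baseline category. The conflict over the role of surgery between sections IV.A and IV.F can be read directly from the text. This should be fixed before analysis; it does not make the planned tests invalid.

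**What to change.** Replace the censoring sentence in section IV.F with:

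> Surgery is a competing event for the operated extremity. The cumulative incidence of re-epithelialization without surgery (Aalen-Johansen) will be shown by arm in place of one minus Kaplan-Meier, with the cumulative incidence of surgery beside it. The log-rank test and Cox model remain primary, are interpreted as cause-specific hazard analyses, and are stratified by the randomization severity category (and age, if used in randomization). Sensitivity analysis: Gray's test or a Fine-Gray model, with operated burns counted as not healed to a horizon fixed in advance.

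Also:
- Reconcile sections IV.A and IV.F so that surgery has one stated role.
- Assign a stratum to averaged scores that section IV.C leaves without one: 4.5 and 7.5, and also 1, 1.5, 9.5 and 10 if such burns can enter.
- Keep the rule per extremity. Section IV.B says "Each injured extremity will serve as a separate data point", while the present rule censors patients.

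The cost is SAP wording and standard software. Surgery dates are already needed for the present rule, and the severity category is already recorded. There are downsides. The analysis is a little longer and the healed proportion will read lower. Where surgery takes slow healers within a category at different rates by arm, the stratified test can give more false wins than the unstratified one (about 11–12% against 4% in the assumed case), so the primary result must be read beside the two cumulative incidence curves. The sensitivity analysis responds to surgery rates as well as healing and so tilts toward the arm with less surgery, which is why it should not be primary.

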
brown or black in color, dry appearing; 10) Fourth degree- third degree + muscle and or bone involvement. The provider and burn nurse will each give the patient a number and the severity will be determined based on the average of the 2 numbers. Any patient given a number 2, 3 or 4, will be placed into the "partial thickness" category, any patient given a 5, 6, or 7 will be placed into the "deep partial thickness" category, and lastly, any patient given an 8 or 9 will be placed into the "full thickness" category for burn severity.

Patients will be randomized into one of two groups, Mepitel Ag or standard TAO, using RedCap and based on a random clinical trial excel spread sheet balanced by burn severity. A statistician will provide a randomization scheme for investigators to follow. Photographs will be taken prior to dressing application at the initial visit and each subsequent visit. ~~Patient wounds will be dressed in either Mepitel Ag, kling or kerlex, cast padding, gypsoma plaster, soft cast material and coban for up to 21 days or until complete re-epithelialization of the wound occurs or unless surgery is indicated; the control, standard dressing of Triple Antibiotic Ointment impregnated adaptic gauze, kling or kerlex, cast padding, gypsoma plaster, soft cast material and coban for 10-14 days, or Nystatin impregnated adaptic, kling or kerlex, cast padding, gypsoma plaster, soft cast material and coban for 8-21 days or until complete re-epithelialization of the wound occurs or surgery is indicated. The SCT is applied by Occupational and Physical trained in casting and positioning. The soft cast provides optimal positioning while eliminating friction on the burn area. Dressing changes will occur every 3-10 days and will be determined by the provider, based on burn wound severity. Upon each return clinic visit, the patient will have their wound severity assessed by the following scoring system: 1=0% healed, 2=20% healed; 3=40% healed; 4=60% healed; 5=80% healed; 6=100% healed. This will be established by provider and burn nurse examination of the wound. This will be recorded in RedCap:_____~~

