A member of the nursing team will also complete a questionnaire at each follow up visit to indicate pain level with dressing change based on the FLACC scale, parents perceived level of pain during dressing change, parental reported pain level at home, use of home pain medications, type of home pain medication- narcotic vs non-narcotic, clinical assessment of yeast rash including odor, visible rash, use of fluconazole, ease of dressing application, and amount and type of product used in dressing change.

D. Description, Risks and Justification of Procedures and Data Collection Tools:

A photography release will be distributed and signed by parent at initial visit.

Anursing questionnaire will be completed by nursing staff at each follow up appointment.

Local wound care including cleansing, wound measurement and dressing change will be performed by burn team including nursing staff and occupational and physical therapists. Although punch biopsy with histological analysis is considered the 'gold standard' in assessing burn wound depth, it is invasive and time consuming.¹⁸ Clinical assessment remains the most frequent and rapid method.¹⁸ Due to the time sensitive nature of the proposed trial and in order to avoid delaying wound care and initial dressing application, a 10 point clinical assessment scale has been created, as listed above for use in determining initial burn wound severity. Patient wound depth will be clinically determined by the average of the scores from the provider and the burn nurse.

The wound will also be assessed by the provider and nurse on subsequent visits using the following scoring tool: 1=0% healed, 2=20% healed; 3=40% healed; 4=60% healed; 5=80% healed; 6=100% healed. This will be established by provider and burn nurse examination of the wound. This will be recorded in RedCap.

The overall risk for this study is minimal, with no foreseen adverse reactions. The risk of a silver allergy or adverse reaction to silicone is very rare.

E. Potential Scientific Problems:

Limitations to the proposed study design include varying diagnostic opinions between provider and burn nurse for the determination of superficial vs deep partial thickness burn wounds based on clinical assessment, provider or nurse bias based on dressing preference, and possible uneven trial groups.

F. Data Analysis Plan:

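### Pain is scored at every follow-up visit, but section IV.F names only unadjusted two-sample tests and does not say which visit or summary they compare

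*Combined protocol and SAP*

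**What the plan says.** Section IV.C (Study Design and Research Methods) makes pain a repeated measure: "A member of the nursing team will also complete a questionnaire at each follow up visit to indicate pain level with dressing change". The same questionnaire covers "parents perceived level of pain during dressing change, parental reported pain level at home, use of home pain medications".

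The number of visits is not fixed. Background and Significance says of the current control dressing: "This dressing is applied two to three times during the first 2 weeks post injury". Section IV.C adds "Dressing changes will occur every 3-10 days and will be determined by the provider, based on burn wound severity", with treatment in the Mepitel Ag arm "for up to 21 days or until complete re-epithelialization of the wound occurs", or until surgery. These two statements from IV.C stand in text that carries strike-through marks in the copy reviewed, which may be a conversion effect, so the point does not rest on them. Section IV.A lists the number of clinic visits and of soft casts among the outcomes.

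Section IV.F (Data Analysis Plan) gives one sentence on the analysis: "Pain level outcomes and pain medication use will be compared using two-sample t-tests and chi-squared tests". Section IV.B defines the data point: "Each injured extremity will serve as a separate data point". Section IV.C uses burn severity and age in the randomisation (one paragraph there mentions severity alone), but the pain tests adjust for neither.

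**The concern.** A two-sample t-test or a chi-squared test takes one independent value per unit. Each child will supply several pain scores, and how many depends on how long the wound takes to heal, which is the primary outcome. The visit count is therefore a post-randomisation variable, and the trial's own hypothesis predicts that it differs between arms. The control dressing also changes after the first two weeks (Background and Significance), so a summary over all visits can mix dressings in proportions that depend on healing speed.

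Less pain at dressing changes is one of the three benefits claimed in the hypothesis (section I) and again in section IV.G. If the value compared is not fixed in advance, the analyst can choose among the first, worst, mean or pooled scores after seeing the data. Some of those choices change the error rate or the estimate.

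**Working it through.** **The plan's own figure.** There is none for pain. The only power statement (IV.F) concerns healing time: a 2-day difference, SD 0.3, 50 per group. The standard error is 0.3 × √(2/50) = 0.06, and 2/0.06 = 33.3 standard errors, so power is essentially 100%. That agrees with the stated figure of over 90%. Only the 2 days and the 50 per group are used below.

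**Assumed inputs, because the documents give none:** within-child correlation (ICC), pain SDs, pain trajectory and visit distribution. Tests are taken as two-sided at 0.05, since sidedness is not stated.

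**1. How many visits?** Two to three applications in 14 days means one every 14/3 = 4.7 to 14/2 = 7 days. Background and Significance also says that a cast can stay on for 7-10 days. A range of 2-4 visits per child is used.

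**2. Visits pooled as independent.** With m visits per child, the design effect is DE = 1 + (m − 1) × ICC, and the actual type I error is 2 × [1 − Φ(1.96/√DE)].
- m = 2, ICC 0.3: DE = 1.3, error 8.6%.
- m = 3, ICC 0.5: DE = 2.0, error 16.6%.
- m = 4, ICC 0.6: DE = 2.8, error 24.1%.

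A simulation with 50 per arm, 2-4 visits and the same visit distribution in both arms gave 12.5% (ICC 0.3) and 17.4% (ICC 0.5) with flat pain. With pain falling 1 point per visit it gave 11.3% and 14.6%.

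**3. Visits averaged per child.** If pain falls s points per visit, a child with k visits has mean score (start) − s(k − 1)/2. With identical pain in both arms at every visit, the faster-healing arm looks worse by (s/2) × (difference in mean visits).
- Visit gap implied by the planned effect: 2/10 = 0.2 to 2/4.7 = 0.4 visits. The scenario of 2.7 vs 3.0 (gap 0.3) lies in the middle.
- s = 1: 0.5 × 0.3 = 0.15 points. s = 2: 1.0 × 0.3 = 0.30 points.
- Simulated rejection (start score 6, between- and within-child SD 1.5, 50 per arm): 7-11%. Re-runs with other assumed visit distributions gave 6-13%.
- Hand check: the variance of a child's mean is about 1.5² + 1.5²/2.85 = 3.04, so the standard error is √(3.04 × 2/50) = 0.349. The biases are 0.43 and 0.86 standard errors, giving rejection of about 7% and 14%. Spread in visit numbers adds variance that this check leaves out, so the upper figure is a little high.
- s = 0: bias zero. s negative (pain rises): the sign reverses and the faster-healing arm looks better. With 2.5 vs 3.5 mean visits and a rise of 0.5 per visit, the formula gives 0.25 × 1.0 = 0.25 points, and the simulation gave 0.25.
- Same visit distribution in both arms: rejection 4.6-5.4%, so no inflation.

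**4. One prespecified visit.** The t-test at the first follow-up dressing change rejected in 4.2-5.7% of simulated null trials in every scenario, including unequal visit numbers and falling pain. The mixed and GEE models proposed below were not simulated.

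**The case against.** The strongest reply is that the plan nowhere says visits will be pooled or averaged. A t-test at one stated visit is a legitimate reading, and it keeps its error rate. Pooling also fits the documents poorly, because IV.B and IV.F count extremities, subjects and burns rather than visits. This stands. A reader might infer that the stated tests cannot give a valid answer however they are applied; the documents do not support that.

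The averaging bias is also conditional. The documents give no pain trajectory. They describe painful removal when gauze dries out and disturbs new epithelium, and such pain need not fall from visit to visit. A reader might infer that Mepitel Ag will be penalised if it heals wounds faster. That needs both falling pain and a gap in visit numbers.

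The reply does not supply what is missing. The plan names no visit and no summary, and its tests ignore both the visit count and the randomisation factors. Pain being a secondary outcome lowers the priority but does not settle which number will be compared.

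**Conclusion.** The point holds as under-specification with a cheap and better alternative. The plan is not wrong as written. Only the missing visit, summary and repeated-measures method are certain; the harm depends on a choice that the plan leaves open. Pooling would give about 9-24% type I error, for 2-4 visits and an assumed ICC of 0.3-0.6. Averaging would give a bias of 0.15-0.3 points and about 7-11% rejection, if pain falls 1-2 points per visit and the arms average 2.7 and 3.0 visits. A single prespecified visit gives no inflation.

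A larger averaging effect is tempting. With 2.5 vs 3.2 visits the same assumptions give 0.35-0.7 points and 17-46% rejection. But a 0.7-visit gap from a 2-day effect needs a dressing change every 2/0.7 = 2.9 days, at the short end of the 3-10 day range, or a healing effect well beyond the planned one. It should not be taken as the expected size. Confidence is high that the analysis is under-specified and low on the direction of any harm.

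**What to change.** In IV.F:
- Make FLACC at the first dressing change after randomisation the main pain comparison, by linear regression on arm, severity stratum and age. Nearly every child should have this visit, and it does not depend on how many visits follow.
- Analyse all visits with a linear mixed model: arm, days since injury, severity and age, with a random intercept for child and extremity nested within child where both are injured. This compares the arms at the same time since injury. Because visits stop at healing, it assumes that earlier scores and the covariates account for who is still being dressed.
- Analyse medication use with a GEE logistic model clustered by child.
- Where a child contributes two extremities, base the main comparison on one value per child or use a standard error clustered by child. This clustering is a separate layer from repeated visits.

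The cost is a few lines of text and slightly more analysis work, on data already being collected. The downside is that the main comparison covers only the first dressing change; the mixed model carries the later ones.

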A review of the current literature demonstrates silver sulfadiazine (SSD) to be the most frequently used dressing for burn wound treatment in many clinics nationwide.²⁸ The use of SSD is associated with once to twice daily painful dressing changes and wound exposure that "may lead to disruption of newly formed epithelium, wound colonization, subsequent wound infection and deepening of the burn".^{23, 28} One major benefit of the SCT is the reduction in

required dressing changes, as the soft cast can stay in place for 7-10 days while maintaining optimal hand or foot positioning. This eliminates the need for frequent painful dressing changes.

Occasionally, We have observed yeast infections when patients require serial casting and all have been treated with antibiotics. Other complications we have experienced include: occasional drying out of the adaptic gauze leading to a painful dressing removal and interruption of the newly epithelialized wound bed.

Mepitel Ag, a new soft silicone dressing produced by Molnlycke Health Care, combines Safetac technology with a silver compound to provide a broad spectrum of antimicrobial coverage. The safetac technology “protects the wound and the skin. It prevents an outer dressing from sticking to the wound, therefore minimizes trauma and pain”.¹⁵ The highly pliable nature and antimicrobial properties of the dressing make it an ideal alternative to TAO and SSD for the treatment of pediatric partial to deep partial thickness hand and foot burns. The silver compound lasts up to 8 days, while minimizing damage to the new epithelium and creating a moist wound environment. As Mepitel Ag is a relatively new product, there are currently no studies analyzing its efficacy and effectiveness when compared to other burn treatment methods.

The aim of this study is to compare Mepitel Ag to triple antibiotic ointment impregnated Adaptic gauze when used with the soft cast technique to assess overall time to healing, yeast infection rate and parents perception of pain level at time of dressing change on a scale of 1-10. The hypothesis is that Mepitel Ag in combination with the soft cast technique improves wound healing in pediatric partial to deep partial thickness hand and foot burns by decreasing the length of healing time, decreasing the risk of yeast infection, and decreasing pain associated with dressing changes.

III. Preliminary Studies/Progress Report:

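### The only justification for 100 burns rests on an SD of 0.3 with no unit; read as days it is not credible and makes the stated power uninformative

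*Combined protocol and SAP*

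**What the plan says.** The combined protocol and SAP justifies its sample size in one place, Section IV.F.1. It assumes a "standard deviation of 0.3, alpha of 0.05 and 50 subjects per group there is over 90% power to detect a difference of 2 days" and concludes that "we expect that our proposed sample size of 100 burns will be adequate for the main objective of this study". The assumptions are attributed to reference 22, which the reference list (IV.H) describes as an unpublished abstract; none of its results are reproduced. The paragraph does not name the test or say whether alpha is one- or two-sided.

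Other sections bear on the figure:

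- **Outcome (IV.A).** The primary outcome is "measured in length of days to re-epithelialization or need for surgical intervention".
- **Population (IV.B).** Patients are "between the ages of 31 days and 18 years with newly diagnosed partial to deep partial or full thickness hand or foot burns", and "Each injured extremity will serve as a separate data point".
- **Assessment (IV.D).** The provider and nurse score percentage healed at return visits. The background section says that "the soft cast can stay in place for 7-10 days while maintaining optimal hand or foot positioning".
- **Analysis (IV.F).** For time to healing, "we will use Kaplan-Meier curves, the log-rank test and a Cox proportional hazards model". "Patients that require surgical intervention will be censored at the time of surgery".

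**The concern.** The SD is the one input that turns a 2-day difference into a power figure, and it is printed without a unit beside a difference in days. The natural reading is 0.3 days, about 7 hours. On that reading 50 per group is far more than the calculation needs, so the calculation cannot be the reason for 100 burns. That spread also conflicts with the population and the way healing is observed.

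Nothing else in the document supports the sample size, and nothing lets a reader recover the intended input: no mean healing time, hazard ratio, event count or expected surgery rate is given. If the true SD is well above 3 days, the trial could miss a 2-day benefit while claiming more than 90% power to find it, and a null result would be misread.

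The same paragraph moves from subjects per group to a total in burns. Because a child with bilateral injury contributes two data points, these are different units.

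**Working it through.** **Inputs.** From IV.F.1: SD 0.3, alpha 0.05, n = 50 per group, difference 2 days. Assumed here, because the plan does not say: a two-sided, two-sample t-test and, first, an SD in days. Power comes from the noncentral t distribution with 2n − 2 degrees of freedom and noncentrality d·√(n/2), where d = difference/SD.

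**1. The plan's own figure.** d = 2/0.3 = 6.67 and the noncentrality is 6.67 × √25 = 33.3. Power is 100% to any printed precision, so the statement of more than 90% is reproduced.

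**2. What those inputs would justify.** With d = 6.67, power is 89.1% at 2 per group and 99.99% at 3 per group. At 50 per group, 90% power needs d = 0.6548, which is 0.6548 × 0.3 = 0.196 days, or 4.7 hours.

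**3. Is 0.3 days possible under this design?**

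- If healing is recorded in whole days, the largest share p of an arm that can fall off the commonest day solves p(1 − p) = 0.3² = 0.09, so p = 0.10. At least 90% of the arm would have to heal on the same day.
- If 49 of 50 burns are recorded healed at one visit and one burn k days later, the sample SD is k × √(1/50) = 0.141k. For k = 7 this is 0.99 days, and for k = 10 it is 1.41. For k = 3, the shortest dressing-change interval in the IV.C text that appears struck through, it is 0.42. One late burn in 50 exceeds 0.3 in each case.

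**4. Power for 2 days at 50 per group, by assumed SD.** The largest SD that keeps 90% power is 2/0.6548 = 3.05 days.

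| Assumed SD (days) | d | Power |
|---|---|---|
| 2.1 (0.3 weeks) | 0.95 | 99.7% |
| 3.0 (decimal slip) | 0.67 | 91.0% |
| 3.5 | 0.57 | 80.8% |
| 4 | 0.50 | 69.7% |
| 5 | 0.40 | 50.8% |
| 6 | 0.33 | 37.9% |

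**5. If 0.3 is an SD on the log scale.** Then d = ln(control/treated)/0.3, and power depends on healing times that the plan does not give.

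| Assumed typical healing (days) | d | Power |
|---|---|---|
| 10 vs 8 | 0.744 | 95.8% |
| 11 vs 9 | 0.669 | 91.2% |
| 12 vs 10 | 0.608 | 85.3% |
| 14 vs 12 | 0.514 | 72.0% |

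**6. The planned analysis is log-rank/Cox, not a t-test.** As an illustration only, I simulated a 2-day shift with SD 3.0 days, 50 per group and no censoring (40,000 runs). Log-rank power was 78.9% for right-skewed times, 85.5% for normal times and 98.6% for left-skewed times with proportional hazards, against 91.0% for the t-test. Rejection under no difference was 5.3–5.5%. The t-test figure therefore does not carry over in either direction.

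Under proportional hazards with 1:1 allocation, the hazard ratio detectable with 90% power is exp(2 × 3.2415/√events): 1.91 for 100 healing events, 1.98 for 90 and 2.06 for 80. Censoring at surgery reduces the number of events, and the plan gives no expected number.

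**The case against.** The strongest reply is that no sum is wrong: the stated power follows from the printed inputs. The fault lies in an input, and its unit and scale may be clear in the cited abstract. Several readings also leave the conclusion intact: 3.0 days gives 91%, 0.3 weeks 99.7%, and a log-scale SD of 0.3 gives 96% for 10 versus 8 days. This stands, and it is why the point does not allege underpowering. But none of those readings is confirmed, and under a decimal slip the margin is thin, since 90% is lost just above 3.05 days.

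The credibility argument can also be pressed. The 7–10 days in the background section describes how long a cast can stay on, not a visit schedule. The 49-of-50 example assumes that healing is dated to the visit and that burns share visit days. Censoring surgical cases may narrow the spread among burns observed to heal. These are fair limits. Even so, a 3-day gap gives 0.42 days, and nothing in the document suggests a spread near 0.3 days across this range of depths and ages.

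Finally, IV.F.1 openly presents its calculation as a simplification, so the gap between a comparison of means and the log-rank/Cox analysis is partly disclosed. That is true, but the adequacy of 100 burns is still asserted for the main objective, which that analysis serves. The simulated and hazard-ratio figures are guides only; they rest on assumed shapes and event counts.

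**Conclusion.** The concern holds. The only support for 100 burns uses an SD with no unit which, read as days, is not credible and makes the power statement uninformative. Confidence is high on both points.

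The plan does not establish whether the trial is well powered or underpowered for 2 days. At 50 per group, power is at least 90% only if the SD is about 3.05 days or less, and it falls to 70% at 4 days and 38% at 6. All SDs and healing times other than the printed 0.3 are assumptions, as is the two-sided test; a one-sided alpha of 0.05 would give about 80% rather than 70% at an SD of 4 days. The figures treat burns as independent and ignore censoring. This should be corrected, because the main objective depends on it.

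**What to change.** Rewrite Section IV.F.1 as follows:

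- Check the SD against the cited abstract. State its value, its unit or scale, and the source figure it comes from.
- Name the test and the sidedness of alpha. Restate the power of 50 per group for a 2-day difference, with a short table over a range of SDs.
- Say whether the 50 per group are subjects or burns.
- Give the power of the planned log-rank/Cox analysis, with stated assumptions on the number of healing events, censoring at surgery and the shape of healing times.
- If the restated power is below 90%, say so.

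The cost is checking one source and rewriting one paragraph. The stated power may become less favourable. No change in enrolment is requested.
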